### **5.7.4. Analyses of Exploratory Efficacy Variables**

The exploratory efficacy endpoints listed in Section 4.4.3 will be analyzed in the same method as the analysis method used for primary endpoint and secondary endpoint.

### **5.7.5. Subgroup Analysis**

Subgroups described in Section 3.6 for the primary and key secondary efficacy endpoints listed in Section 4.4.1 and Section 4.4.2 will be analyzed. The analysis method for the subgroup analysis will be conducted using the primary analysis of continuous and category endpoints described in Section 5.7.1 and Section 5.7.2. Interactions between the subgroups and treatment groups will also be tested.

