### **3.6. Subgroups**

Subgroups are defined by key baseline factors recorded on the CRF and listed as follows

Subgroups to be considered for efficacy/safety analyses:

- Age group ( $\geq 18$ - $<40$ ,  $\geq 40$ - $<65$ ,  $\geq 65$ )
- Sex (Male, Female)
- Baseline weight group ( $<70$  kg,  $\geq 70$ - $<100$  kg,  $\geq 100$  kg)

93% patients enrolled for this study are white so no subgroup for ethnicity or race as all patients are not Hispanic or Latino

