#### 4.4.2. Secondary Efficacy Variables

The secondary endpoints are:

- Percent change in weekly Eosinophilic Esophagitis Activity Index (EEsAI) PRO score from baseline to week 10
- Change in weekly EEsAI PRO score from baseline to week 10
- Percent change in weekly EEsAI PRO score from baseline to week 12
- Change in weekly EEsAI PRO score from baseline to week 12
- Percent change in the SDI PRO score from baseline to week 10
- Percent change in the SDI PRO score from baseline to week 12
- Change in the SDI PRO score from baseline to week 12
- Change in EoE-QOL-A PRO score from baseline to week 12
- Percentage of patients with SDI PRO response at week 10; where response is defined as a decrease of at least 3 points on the SDI compared to baseline
- Percentage of patients who achieve  $\geq 40\%$  improvement in EEsAI score from baseline to week 10
- Percent change in overall peak esophageal intraepithelial eos/hpf (400X) from baseline to week 12
- Change in EoE-EREFs (endoscopy visual anatomical score) from baseline to week 12
- Percentage of patients with use of rescue medication or procedure (eg, esophageal dilation) through week 12
- Incidence of treatment-emergent AEs

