### **5.7.3. Analyses of Secondary Efficacy Variables**

The continuous secondary efficacy endpoints listed in Section 4.4.2 will be analyzed using the same approach as that used for the analysis of the primary endpoints. Inside step 2 of MI procedure, the missing data at subsequent visits will be imputed using the regression method for the monotone pattern with adjustment for covariates including treatment groups, baseline SDI score and relevant baseline value. Data of each of the 50 complete datasets will be analyzed using an analysis of covariance (ANCOVA) model with treatment group as fixed effect, and the baseline SDI value and relevant baseline value as continuous covariates.

Due to the substantial imbalance at baseline in the number of patients in the two randomization strata (only 12.8% patients in the strata of baseline SDI > 7), the imputation and ANCOVA will not use randomization strata as a factor. Instead the model includes the baseline SDI score as a continuous covariate.

Categorical analyses will be performed on responder data. Comparisons between dupilumab and placebo will be done using the Fisher exact test. Patients with early withdrawals or use of rescue medication or procedure will be counted as non-responders.

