## 10. APPENDIX

### 10.1. Summary of Statistical Analyses

#### Efficacy Analysis:

| Endpoint   | Analysis Population | Primary Statistical Method                              | Supportive/Sensitive Statistical Method   | Subgroup Analysis | Other Analyses |
|--|---------------------|---|---|-------------------|----------------|
| Change in the SDI score at week 10 from baseline | FAS                 | MI + ANCOVA   | MI+ANCOVA regardless of rescue, ANCOVA on LOCF, WOCF and OC, and primary efficacy analysis on PPS | Yes               | Line plot      |
| Secondary continuous variables                   | FAS                 | MI + ANCOVA   | NO  | No                | Line plot      |
| Categorical variables                            | FAS                 | Fisher exact test / define missing as treatment failure |   | No                | Histogram      |
|  |                     |   |   |                   |                |

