**Safety Analyses:**

| Endpoint            | Analysis Populations | Statistical Method     | Supportive Analysis | Subgroup Analysis | Other Analyses |
|---------------------|----------------------|------------------------|---------------------|-------------------|----------------|
| Adverse Events      | SAF                  | Descriptive statistics | No                  | No                | No             |
| Laboratory Measures | SAF                  | Descriptive Statistics | No                  | No                | No             |
| Vital sign          | SAF                  | Descriptive Statistics | No                  | No                | No             |
| ECG                 | SAF                  | Descriptive Statistics | No                  | No                | No             |

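### Section 5.7.5 orders subgroup and interaction tests for undefined key secondary endpoints that Appendix 10.1 excludes, and it does not supply a workable interaction method

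*SAP*

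**What the plan says.** Section 3.6 defines three factors: age (three levels), sex (two) and baseline weight (three).

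Section 5.7.5 states that these subgroups "for the primary and key secondary efficacy endpoints listed in Section 4.4.1 and Section 4.4.2 will be analyzed". It gives the method as "using the primary analysis of continuous and category endpoints described in Section 5.7.1 and Section 5.7.2", and adds: "Interactions between the subgroups and treatment groups will also be tested". It writes no interaction model.

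Section 4.4.2 opens with "The secondary endpoints are" and lists 14 items: 10 continuous efficacy endpoints, 3 categorical efficacy endpoints and the incidence of treatment-emergent adverse events. None is singled out as key.

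The efficacy table in Appendix 10.1 has a subgroup column. It reads Yes for the primary endpoint, No for the row "Secondary continuous variables" and No for the row on categorical variables.

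The only categorical test in the plan is in Section 5.7.3: "Comparisons between dupilumab and placebo will be done using the Fisher exact test". Section 5.7.5 does not cite 5.7.3.

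Section 5.7.2 imputes the missing data of the FAS 50 times. The imputation model contains treatment, baseline SDI and the observed values from clinic visits up to week 10. The ANCOVA contains treatment and baseline SDI.

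**The concern.** Two parts of the same plan give opposite instructions on whether secondary endpoints receive subgroup and interaction tests, and the word that should limit the set, key, has no definition. Section 7 makes the analyses at the first database lock final, and an unblinded team performs them. If the conflict stands until then, the set of secondary endpoints with subgroup p-values can be chosen with results in hand.

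The method has two further gaps. For categorical endpoints an interaction test is ordered but none is available. For the primary endpoint, an interaction would be tested on data completed by a model that assumes no interaction, which favours finding none.

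**Working it through.** **1. The plan's own figure.** The SAP gives no figure for the subgroup tests. Its sample-size figure (Section 2.2) concerns the primary comparison and reproduces. With 18 per arm, a difference of 3 and SD 2.46, the noncentrality is 3 / (2.46 × √(2/18)) = 3 / 0.82 = 3.66 on 34 df. Two-sided 5% power is 94.4%, against 94% stated. Dropout: 18 / 0.85 = 21.2, so 22 per arm, as stated. Nothing below alters this.

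**2. The instructions side by side.**

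| Endpoint group | Section 5.7.5 | Appendix 10.1 |
|---|---|---|
| Primary (SDI change, week 10) | subgroups and interactions | Yes |
| 10 secondary continuous | subgroups and interactions if key | No |
| 3 secondary categorical | subgroups and interactions if key | No |

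The two agree on the primary endpoint. They conflict on the secondary endpoints, unless key is read as an empty set.

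**3. Number of interaction tests**, one per factor and endpoint:
- Appendix 10.1: 3 × 1 = 3.
- Section 5.7.5 with key read as all 13 efficacy endpoints: 3 × (1 + 13) = 42.
- Of the 39 extra tests, 3 × 10 = 30 are on continuous endpoints and 3 × 3 = 9 on categorical endpoints, for which the plan has no interaction test.

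If the 30 continuous tests were run at 5% (the SAP states no level for them) and no interaction existed, 30 × 0.05 = 1.5 false positives would be expected. This is the upper case, because key normally means a subset.

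**4. Categorical method.** Section 5.7.1 holds a rule that counts patients as non-responders after rescue, but no test. Section 5.7.2 is MI with ANCOVA for a continuous score. The Fisher exact test in 5.7.3 compares two arms in one table. It can be repeated within each level, but it does not test whether the treatment effect differs between levels.

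**5. Imputation and the primary-endpoint interaction.** Let the true effects in two levels be a and b, the share of week 10 scores missing be m in every cell, and the pooled effect be p. If imputation used only treatment and baseline, the expected effects after imputation would be (1 − m)a + mp and (1 − m)b + mp. Their difference is (1 − m)(a − b), so the interaction shrinks by the factor 1 − m. The SAP does not give m. Purely as an illustration, its 15% dropout assumption would give 0.85. The pull should be weaker than this, because patients' own earlier scores are in the imputation model and carry part of any subgroup difference. It could be stronger if diary failures (Section 4.4) make m larger.

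**6. Sparse levels.** Level counts are not given. Assuming 47 patients split 24/23, the chance that all k patients of a level fall in one arm is [C(24,k) + C(23,k)] / C(47,k): 49%, 23% and 11% for k = 2, 3 and 4. No rule covers this case.

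**The case against.** The best defence is that these are supportive analyses in a proof-of-concept trial. No decision depends on an interaction p-value, the primary test is untouched, and low power for interactions is generic at this size. Section 5.7.1 also calls the appendix a summary, so the text could be taken to govern. All of this limits the weight of the point. It does not remove it: even if the text governs, key remains undefined and the method reference still fails.

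Several stronger readings are tempting, and the documents do not support them:

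- **That the prescribed model cannot be fitted in three-level subgroups.** Section 5.7.2 imputes from the whole FAS; it does not prescribe imputation within levels. The ANCOVA has three mean parameters, and an average level would hold 13.0, 14.7 or 15.7 patients for totals of 39, 44 or 47. Read literally, clinic visits up to week 10 are weeks 1 to 4 and 8, so the imputation regression has 8 coefficients (intercept, treatment, baseline SDI, five visits), not the 12 that all weekly scores would give. Failure in a sparse level is possible but not shown.
- **That 47 patients were enrolled.** This is only an inference from the 12.8% in Section 5.7.2: 6/47 = 12.77%, but 5/39 = 12.82% fits too, and 44 were planned.
- **That a false positive is 86% likely.** The figure 1 − 0.95^39 = 0.865 counts the 9 categorical tests that the plan cannot perform. It also assumes independence, although many endpoints are change and percent change of the same score.
- **That the safety sections contradict each other.** Section 3.6 says "Subgroups to be considered for efficacy/safety analyses", which is permissive. Section 5.8 orders no safety subgroup analysis, so No in every row of the "Subgroup Analysis" column of the safety table is compatible with it.

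**Conclusion.** The plan is wrong as written on three counts. Section 5.7.5 and Appendix 10.1 cannot both be followed for secondary endpoints, so the number of interaction tests is 3 or anything up to 42. The cited sections hold no categorical test, and the one that exists elsewhere cannot test an interaction. The imputation model for the primary endpoint omits the subgroup and its interaction with treatment, so a tested interaction tends towards zero by an amount that the SAP does not allow one to quantify.

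The count of 42 rests on three factors and on reading key as all 13 efficacy endpoints. The direction of the imputation pull rests on some week 10 scores being missing, which Section 4.4 makes likely. The primary comparison is unaffected. Severity is minor: a repair of consistency and method for supportive analyses.

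**What to change.** 1. Delete the reference to key secondary endpoints from Section 5.7.5, so that it matches Appendix 10.1. Alternatively, name the chosen endpoints in both places, cite Section 5.7.3, and state an interaction test for any categorical endpoint retained.
2. Write the interaction model for the primary endpoint: the ANCOVA of Section 5.7.2 plus the subgroup factor and its interaction with treatment, one factor at a time.
3. For that test only, run a separate FAS imputation that includes the subgroup factor and its interaction with treatment. Leave the imputation for the primary analysis unchanged.
4. Set a minimum level size, fixed before unblinding, below which results are descriptive only.

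The age and weight categories can stay. Replacing them with continuous terms is a trade-off, because it assumes linearity, and this point does not require it.

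The cost is SAP wording and modest programming, with no new data. The downsides are no subgroup p-values for secondary endpoints (under the first option in step 1) and a slightly larger imputation model for a supportive analysis.

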## **5.8. Analysis of Safety Data**

The summary of safety and tolerance will be performed based on SAF.

The safety analysis will be based on the reported AEs, clinical laboratory evaluations, physical examination, vital signs, and 12-lead ECG.

Thresholds for treatment-emergent Potentially Clinically Significant Values (PCSVs) in laboratory variables, vital signs and ECG are defined in [Appendix 10.3](#). Treatment-emergent PCSV is any PCSV developed or worsened in severity compared to the baseline during the treatment and follow-up period.

The time interval to detect any event or abnormality is between the first injection of study medication and EOS.

### **5.8.1. Analysis of Adverse Events**

The number and proportion of patients will be summarized separately for the week 12 treatment period, the follow-up period, and overall study period, described in Section 3.3. Adverse event (AE) incidence tables will be presented for each treatment group, including the number (n) and

percentage (%) of patients experiencing an AE, where multiple instances of the same event occur in the same patient the event will be counted only once for that patient. The denominator for computation of percentages is the number of patients in each treatment group.

The number and proportion of patients reporting TEAEs will be summarized, sorted by decreasing frequency of SOC and PT for the dupilumab group. The number and proportions of patients reporting TEAEs will also be summarized, sorted by decreasing frequency of SOC, HLT and PT for the dupilumab group.

Patient listings will be provided for all SAEs, death, and TEAEs leading to permanent treatment discontinuation.

The following variables will be included in the listing:

- Patient ID
- Treatment group
- Age/sex/race
- System Organ Class (SOC)
- High Level Term (HLT)
- Preferred Term (PT)
- Verbatim Term
- AE start date and end date/ongoing (using both calendar days and study days)
- AE Duration
- Relationship of AE to study drug: unrelated or related
- Action taken: Dose withdrawn temporarily, Dose reduced, Dose withdrawn permanently, Dose not changed, Not known or Not applicable
- Severity: using a 3-point scale (mild, moderate, or severe)
- Treatment: none, medication, surgery or others
- Outcome: recovered/resolved, recovered/resolved with sequelae, recovering/resolving, not recovered/not resolved, fatal or unknown

#### Overall TEAE summary

The overall summary of TEAEs will be provided with number and proportions of patients with any:

- TEAE
- TEAE related to study drug
- Serious TEAE
- TEAE of special interest (AESI)
- TEAE leading to death

- TEAE leading to permanent treatment discontinuation

AESI

- Anaphylactic reactions
- Acute allergic reactions that require immediate treatment
- Severe injection site reactions that last longer than 24 hours
- Mycosis fungoides
- Cutaneous T-cell dyscrasia
- Any severe infection
- Any infection requiring treatment with parenteral antibiotics
- Any infection requiring treatment with oral antibiotics/anti-viral/anti-fungal for longer than 2 weeks
- Any clinical endoparasitisis
- Any opportunistic infection
- Suicidal behavior

[Appendix 10.5](#) provides a list of AESIs search criteria.

TEAE Incidence

Number and proportions of patients reporting TEAEs will be summarized for the following TEAEs:

- TEAEs
  - TEAEs by SOC/PT
  - TEAEs by SOC/HLT/PT
  - TEAEs by PT
  - TEAEs by SOC/HLT/PT with HLT  $\geq 5\%$  in any treatment groups
  - TEAEs by SOC/PT with PT  $\geq 5\%$  in any treatment groups
  - TEAEs by severity by SOC/PT
  - Severe TEAEs by SOC/PT
  - Severe TEAEs by SOC/HLT/PT
  - TEAEs related to study medication as assessed by the investigator by SOC/PT
  - Severe TEAEs related to study medication as assessed by the investigator by SOC/PT
  - TEAE of special interest/TEAE by category
- Serious TEAEs

- Serious TEAEs by SOC/PT
- Serious TEAEs by SOC/HLT/PT
- Serious TEAEs related to study medication as assessed by the investigator by SOC/PT
- TEAEs leading to permanent discontinuation of study treatment by SOC/PT
- Death by SOC/PT

Summary of the most frequent ( $\geq 5\%$ ) TEAEs by SOC, HLT, PT, respectively, in the dupilumab groups and in the overall study population will be provided.

SAEs/AESI during the Week 12 treatment period, follow-up period, and overall period will be listed.

### **5.8.2. Analysis of Clinical Laboratory Measurements**

Laboratory measurements include clinical chemistry, hematology and urinalysis results, and will be converted to standard international units and US conventional units. Summaries of laboratory variables will include:

- Descriptive statistics of laboratory result and change from baseline by visit
- The number (n) and percentage (%) of subjects with abnormal lab value during study whose screening and baseline values are normal (overall and per each lab parameter)
- The number (n) and percentage (%) of subjects with treatment-emergent PCSVs during study, depending on data
- Shift tables based on baseline normal/abnormal may be used to present the results for parameters of interest

Listing of all laboratory parameters value, normal range, abnormal flag and treatment-emergent PCSV by subject and visit will be provided.

### **5.8.3. Analysis of Vital Signs**

Summaries of vital sign variables will include:

- Descriptive statistics of vital sign variable and change from baseline by visit
- The number (n) and percentage (%) of subjects with treatment-emergent PCSV, depending on data
- Shift tables based on baseline normal/abnormal may be used to present the results for parameters of interest

Listings will be provided with flags indicating the treatment-emergent PCSVs, depending on data.

#### **5.8.4. Analysis of Physical Exams**

The number (n) and percentage (%) of subjects with abnormal physical exams will be summarized at time points according to the schedule in [Appendix 10.2](#), by treatment group. A summary of treatment-emergent abnormal findings will be provided.

#### **5.8.5. Analysis of 12-Lead ECG**

Summaries of 12-lead ECG parameters by treatment group will include:

- Each ECG parameter and change from baseline
- The number (n) and percentage (%) of subjects with PCSV, depending on data
- ECG status (i.e. normal, abnormal) summarized by a shift table

Listings will be provided with flags indicating PCSVs, depending on data.

### **5.9. Analysis of Pharmacokinetic Data**

Due to the sparse nature of the drug concentration data, only descriptive analyses will be performed. Concentrations will be summarized at each time point. Pharmacokinetic variables may include but not limited to  $C_{trough}$  over time,  $C_{last}$  and  $T_{last}$ , as appropriate. Results will be described in the Clinical Pharmacology report.

No formal statistical analysis will be performed.

#### **Impact of Drug Concentration on Safety and Efficacy**

The association of drug concentration and efficacy and/or safety endpoints may be performed, as appropriate.

### **5.10. Analysis of ADA Data**

The ADA variables described in Section [4.6](#) will be summarized using descriptive statistics by treatment arm in the ADA analysis set. Frequency tables of the proportion of patients with pre-existing immunoreactivity, treatment-emergent ADA response, persistent ADA response, and titers will be presented as absolute occurrence (n) and percent of patients (%), presented by treatment groups. Listing of all ADA titer levels and neutralizing antibody status will be provided for patients with a positive response in the ADA assay.

The following summaries will be performed on the AAS:

- Number (%) of patients with pre-existing immunoreactivity, treatment-emergent ADA, and persistent ADA response by treatment group
- Number (%) of patients with ADA peak titer achieved in each of the three ADA Titer value category (Low, Medium and High) as mentioned in Section [4.6](#), by treatment group
- ADA peak titers using descriptive statistics (median, minimum and maximum) for treatment-emergent and persistent ADA response by treatment group

- ADA titers using descriptive statistics (median, minimum and maximum) by treatment group and at each ADA time point analyzed
- Number (%) of patients with NAb status (negative or positive in the NAb assay) in treatment-emergent and persistent ADA response subjects by treatment group

Association between ADA variables (e.g. ADA peak titer, treatment-emergent, persistent ADA responses, and NAb status) and functional dupilumab concentrations may also be explored. plotting and comparing mean functional dupilumab concentrations over time by ADA response (treatment emergent and persistent) and NAb status and by peak titer category.

### **Impact of ADA on Safety and Efficacy**

Analysis of the association of of treatment emergent and persistent ADA response and NAb status with safety endpoints may be performed on SAF.

The safety assessment will primarily focus on the following events:

- Hypersensitivity (SMQ: Hypersensitivity [Narrow])
- Anaphylaxis (SMQ: Anaphylaxis [Narrow])

Number (%) of patients with the above mentioned safety events will be summarized by treatment emergent, persistent ADA response status and neutralizing antibody status during the TEAE period.

Associations between ADA variables (e.g. ADA peak titer, treatment-emergent, persistent ADA responses and NAb status), and efficacy endpoints (clinical response) may be explored by plotting and comparing the mean % change from baseline in clinical response over time by ADA response (treatment emergent and persistent) and NAb status and by peak titer category.

## 6. DATA CONVENTIONS

The following analysis conventions will be used in the statistical analysis.

### 6.1. Definition of Baseline for Efficacy/Safety Variables

Unless otherwise specified, the baseline assessment for all measurements will be the latest available valid measurement taken prior to the administration of study drug. If any randomized patients are not treated, the baseline will be the last value on or prior to the randomization. The following rules specify the determination by both date/time information:

1. For the AE, lab (including biomarker), drug concentration and ADA data, both date and time of the measurement will be used to determine baseline by comparing with the first injection date and time.
2. For other data except AE, lab (including biomarker), drug concentration or ADA, only date of the measurement will be used to determine baseline by comparing with the first injection date.

For the rescreened patients, all data from the same patient will be used to derive baseline regardless if the data is from the screen- failure subject ID or enrolled subject ID.

